8) Analyze the relationship between the change in SIBO and the change in NAFLD-FS at 1 month, 3 months, and 6 months of Compound Zhenzhu Tiaozhi capsule therapy (possible results: unrelated, positively related, or negatively related).

4.6. To estimate the ASCVD risk for all NAFLD patients, and to evaluate whether the therapy of Compound Zhenzhu Tiaozhi capsules improves the risk stratification of ASCVD for NAFLD patients, as well as to compare the therapeutic effects of the study capsules and other conventional drugs. The investigators will estimate the ASCVD risk for NAFLD patients after 1 month, 3 months, and 6 months of

Compound Zhenzhu Tiaozhi capsule therapy, according to *Guidelines for Prevention and Treatment of Dyslipidemia in Adults*.

ASCVD populations with different risk stratifications have different target values of lowering LDL-C / non-HDL-C, as shown in the table below.

Risk Stratification	LDL-C	Non-HDL-C
High-risk	<2.6mmol/L(100mg/dl)	<3.4mmol/L(130mg/dl)
Very high-risk	<1.8mmol/L(70mg/dl)	<2.6mmol/L(100mg/dl)
Note: ASCVD: atherosclerotic cardiovascular disease; LDL-C: low density lipoprotein cholesterol; Non-HDL-C: non-high density lipoprotein cholesterol		

If the baseline of LDL-C is high, as it is difficult to reduce LDL-C level to the basic target value after 3 months of standard treatment with existing lipid-lowering drugs, we propose to lower LDL-C level to at least 50% of baseline as the surrogate target value(IIa recommendation, Level B evidence). There are also some patients at very high-risk who have a baseline LDL-C within the basic target value; for these patients the investigators propose to reduce LDL-C levels to about 30% of baseline (I recommendation, A-level evidence).

Those who meet any of the following criteria can be directly classified as high-risk or very high-risk populations, as indicated:

1. Very high-risk: ASCVD patients (acute coronary syndrome, stable coronary heart disease, revascularization, ischemic cardiomyopathy, ischemic stroke, transient ischemic attack, peripheral atherosclerosis, etc.);
2. High-risk: (1) LDL-C  $\geq 4.9$  mmol/L or TC  $\geq 7.2$  mmol/L, (2) Diabetics: 1.8 mmol/L  $\leq$  LDL-C  $< 4.9$  mmol/L (or) 3.1 mmol/L  $\leq$  TC  $< 7.2$  mmol/L, and age  $\geq 40$  years old.
3. For those who do meet the above criteria, the investigators will evaluate their 10-years ASCVD risk as follows

Number of risk	Stratification of Serum Cholesterol (mmol/L)
----------------	--

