factors	3.1 0 TC<4.1(or) 1.8 ≤ LDL-C<2.6	4.1.TC<5.2(or) 2.6 2 LDL-C<3.4	5.2 ≤ TC<7.2(or)3 .4 2 LDL-C<4.9
Without hypertension	Low-risk (<5%)	Low-risk (<5%)	Low-risk (<5%)
0-1	Low-risk (<5%)	Low-risk (<5%)	Moderate risk (5%–9%)
2	Low-risk (<5%)	Moderate risk (5%–9%)	Moderate risk (5%–9%)
3	Low-risk (<5%)	Moderate risk (5%–9%)	Moderate risk (5%–9%)
hypertension	Low-risk (<5%)	Low-risk (<5%)	Low-risk (<5%)
0	Low-risk (<5%)	Moderate risk (5%–9%)	Moderate risk (5%–9%)
1	Moderate risk (5%–9%)	High-risk (≥10%)	High-risk (≥10%)
2	High-risk (≥10%)	High-risk (≥10%)	High-risk (≥10%)
3	High-risk (≥10%)	High-risk (≥10%)	High-risk (≥10%)

4. If the 10-year ASCVD risk is moderate and the age is less than 55 years old, then the investigators propose to do the remaining life assessment. Those who meet any two of the following items can be classified as high-risk: 1.  $\geq 160$  mmHg or diastolic blood pressure  $\geq 100$  mmHg; 2. non-HDL-C  $\geq 5.2$  mmol/L (200 mg/dl); 3. HDL-C  $< 1.0$  mmol/L (40mg/dl); 4. BMI  $\geq 28$  kg/m^2; 5. history of smoking.

3.5. To assess the quality of life using the SF-36 questionnaire for all NAFLD patients, and to evaluate whether the therapy of Compound Zhenzhu Tiaozhi capsules improves the quality of life for NALFD patients, as well as to compare its therapeutic effects with other conventional drugs.

Patients will be required to fill in the SF-36 questionnaire at the time of enrollment, and after 1 month, 3 months, and 6 months of treatment. SF-36 is one of the most widely used and standardized tools for quality of life assessment. SF-36, as a simple health questionnaire, recapitulates the quality of life of the respondents based on eight categories: physiological function, physical pain, general health status, energy, social function, emotional function, and mental health. The first four categories describe physical health, the latter four describe mental health.

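### Step 3 of the ASCVD stratification in Protocol 4.6 contradicts steps 1 and 2, apparently through a dropped 'not': the 10-year table is opened to patients already classified and closed to the rest

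*Protocol*

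**What the plan says.** Protocol IV, Endpoints, 4.6 opens with the aim "To estimate the ASCVD risk for all NAFLD patients" and goes on to ask whether the capsules improve the risk stratum and how they compare with the other drugs. It names a dyslipidemia guideline as the basis and lists four steps.

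- **Steps 1 and 2** are introduced by "Those who meet any of the following criteria can be directly classified as high-risk or very high-risk populations, as indicated". Step 1 covers established ASCVD (very high risk). Step 2 covers very high LDL-C or TC, and diabetics aged 40 or over within stated lipid ranges (high risk).
- **Step 3** opens the 10-year risk table: "For those who do meet the above criteria, the investigators will evaluate their 10-years ASCVD risk as follows". The table returns low, moderate or high risk.
- **Step 4** starts from a table result: "If the 10-year ASCVD risk is moderate and the age is less than 55 years old", a further assessment is made. Then: "Those who meet any two of the following items can be classified as high-risk".

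ASCVD stratification is also a study aim (Protocol III, items 2 and 3) and an expected result (Protocol, Expected results, items 2 to 4). It appears in neither the primary list (4.1) nor the secondary list (4.2). The SAP text available to me mentions ASCVD only in the abbreviation note under 3.1 and gives no derivation.

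**The concern.** Steps 1 and 2 finish the job for the patients they cover. Step 3 then sends those same patients to a table that can rate them again, and lower. Patients who meet none of the direct criteria are the only ones who still need a rating, and no sentence in either document gives them one. They are also shut out of step 4, because it requires a moderate result from the table.

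The between-group comparison of ASCVD strata is at stake. A programmer who follows the sentence literally produces missing strata for one part of the sample and double, possibly conflicting, strata for the other. A programmer who corrects it silently makes an undocumented choice about an outcome rule in an open-label trial.

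**Working it through.** No sample size, power or test level enters here, and the plan states no figure to reproduce. The check is whether the rule gives each patient exactly one stratum.

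**Inputs, all from Protocol 4.6 (lipids in mmol/L)**
- Step 1: established ASCVD gives very high risk.
- Step 2(1): LDL-C ≥ 4.9 or TC ≥ 7.2 gives high risk.
- Step 2(2): diabetes, age ≥ 40, and either LDL-C from 1.8 to below 4.9 or TC from 3.1 to below 7.2 gives high risk.
- Step 3 table columns: TC 3.1 to 4.1 or LDL-C 1.8 to 2.6; TC 4.1 to 5.2 or LDL-C 2.6 to 3.4; TC 5.2 to 7.2 or LDL-C 3.4 to 4.9. Some comparison symbols are damaged in the text I have, so I took lower limits as included and upper limits as excluded.

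**The two readings.** Let D mean that a patient meets any criterion in steps 1 or 2. As written, the table applies if D holds. With 'not' inserted, it applies if D does not hold.

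**Coverage grid.** I crossed ASCVD (yes/no), diabetes (yes/no) and age (35/50) with LDL-C of 1.5, 2.2, 3.0, 4.0, 5.2 and TC of 2.8, 3.6, 4.6, 6.0, 7.5, keeping pairs with LDL-C below TC.
- Lipid pairs: 2 + 3 + 4 + 5 + 5 = 19. Profiles: 2 × 2 × 2 × 19 = 152.
- D through ASCVD: 4 × 19 = 76.
- D through step 2(1), no ASCVD: 6 pairs × 4 = 24.
- D through step 2(2) only: 13 remaining pairs, less the one with both lipids below the range, for diabetics aged 50: 12.
- D in total: 76 + 24 + 12 = 112. Not D: 152 − 112 = 40.

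| Profiles | As written | With 'not' |
|---|---|---|
| D (112) | All sent to the table: 67 match one column, 25 two, 20 none | Keep the direct stratum and skip the table |
| Not D (40) | No stratum, no access to step 4 | 21 match one column, 15 two, 4 none |

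**Second ratings under the literal rule.** 67 + 25 = 92 profiles are rated twice. Of these, 76 − 12 = 64 have established ASCVD (3 lipid pairs × 4 = 12 match no column). The table has no very-high category, so any result for them differs from step 1. The other (24 + 12) − 8 = 28 are high risk by step 2, and conflict arises only if the table returns low or moderate.

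**Profiles with no column under the literal rule.** The 20 are made up of 8 with both lipids at or above the top limits, 8 with TC above and LDL-C below the table range, and 4 with ASCVD and both lipids below it. One lipid above its limit is not enough: TC 7.5 with LDL-C 4.0 is high risk by step 2(1) but still matches the third column through LDL-C.

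**What remains after inserting 'not'.** Of the 40 profiles, 15 select two columns because TC and LDL-C disagree. Two columns give two strata only where the two cells differ. A further 4 (TC below 3.1 and LDL-C below 1.8) have no column.

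**The case against.** The strongest reply is that this is a slip that no careful reader would follow. That largely stands. The section aims at all patients. Being classed directly makes sense only if the table is for the others. The table's top column ends at TC 7.2 and LDL-C 4.9, exactly where step 2(1) begins. Step 4 raises a moderate result to high, which is pointless for someone already there. A guideline is named as the basis. The intended reading is recoverable from the protocol itself.

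It is also fair that ASCVD risk is not a listed endpoint in the Protocol or an efficacy parameter in SAP 4.1 and 4.2, and that neither the sample size nor the primary analysis depends on it.

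The objection does not remove the defect. The sentence is complete and grammatical, it is an operative rule, and nothing in either document overrides it. Recoverable intent lowers the severity but does not replace a written rule.

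Two stronger readings are tempting and are not supported:
- A reader might infer that every patient with TC ≥ 7.2 or LDL-C ≥ 4.9 falls outside the table. The columns join the two lipids with 'or', so a patient with only one value above its limit can still match through the other.
- A reader might infer that the ASCVD comparison is impossible. That holds only for the literal text. Directly classed patients keep their stratum, and the likely intent is clear.

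**Conclusion.** The contradiction is real and minor. As written, step 3 rates again the patients whom steps 1 and 2 have already classified, and leaves everyone else without a stratum. In the grid this means 40 of 40 profiles unclassified on one side, and on the other 92 of 112 rated twice and 20 of 112 with no column.

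These counts show logical coverage and must not be read as expected patient proportions. The documents do not say what share of patients would meet steps 1 or 2.

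A reader might also infer that restoring one word completes the rule. It removes the inversion, but 15 of the 40 remaining profiles still select two columns and 4 select none.

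The conclusion assumes that no ASCVD derivation exists outside the protocol and SAP text available to me, and that the table limits are as read above. The inversion itself lies in a prose sentence and does not depend on the damaged table symbols.

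**What to change.** Reconcile step 3 with steps 1 and 2 so that the 10-year table applies only to patients not directly classified. In the same edit:

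- State how a patient is assigned when TC and LDL-C select different columns, and when both fall below the lowest column, so that each patient has exactly one stratum. The investigators should settle this from the guideline they name.
- State that the stratum is derived in the same way at baseline and at months 1, 3 and 6 in all four arms. The timing sentence in 4.6 mentions only months 1, 3 and 6 of capsule therapy, although the comparison needs baseline and the other arms.
- List the risk factors counted in the table rows, unless a table note not visible in the text I have already does so.

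The cost is a few sentences in 4.6, with a matching derivation in the SAP if the comparison is to be reported. No extra data, visits or patients follow from correcting step 3, and I see no downside. The edit should be made and dated before the ASCVD strata are compared by arm.

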#### 4. Prescriptions:

4.1: Medications: the dose of Compound Zhenzhu Tiaozhi capsules is 2.52 (4 tablets) tid; metformin is 0.5, tid, and simvastatin is 20mgqn. In general, subjects will be in the hospital for approximately 1 week and continue to receive treatment after discharge from the hospital. The total period of treatment will be 6 months.

4.2: Biochemical assessments: Patients will undergo all the following tests upon admission:

Routine blood test, tumor biomarker tests (alpha-fetoprotein [AFP], carcinoembryonic antigen [CEA], carbohydrate antigen 125 [CA125], and carbohydrate antigen 19-9 [CA19]), uric acid, liver function (representing hepatocyte injury: alanine aminotransferase, aspartate aminotransferase, leucyl aminopeptidase, glutamyl transpeptidase; representing liver secretory function: total bilirubin (TBS), direct bilirubin (DBIL), indirect bilirubin (IBIL); representing liver reserve function: total protein (TP), albumin (ALB), globulin (GLB), and the albumin to globulin ratio (A/G), serum lipid profile (triglyceride, very low density lipoprotein, total cholesterol, low density lipoprotein, high density lipoprotein), FINS (fasting insulin), fasting blood glucose, serum biomarkers of HBV ([i]Hepatitis B surface antigen [HBsAg]; [ii]Hepatitis B surface antibody [anti-HBs]; [iii]hepatitis B e antigen [HBeAg]; [iv]Hepatitis B e antigen antibody [anti-HBe]; [v]Hepatitis B core antibody [anti-HBc]), TP-Ab, syphilis serological test (TRUST), human immunodeficiency virus (HIV), hepatitis C virus antibody,

glycosylated hemoglobin, intestinal mucosal barrier function, coagulation test (prothrombin time [PT], activated partial thromboplastin time [APTT], thrombin time [TT], and fibrinogen [FIB]), Fibrotouch, hydrogen and methane breath test.

4.3 Medical advice on discharge: Physicians need to inform patients regarding the severity of complications in the late stage of NALFD and the importance of early treatment. All the patients should continue treatment after discharge and follow-up in the clinic. They will be required to come back to hospital one month later for re-assessment of the above mentioned items. The appointment telephone number is [name]. The contact doctor is [name].

4.4 All patients will be treated with TLC.

4.4.1 Dietary advice: On the basis of daily nutrient and energy requirements, if the total amount of saturated fatty and trans fatty acids exceeds the recommended upper limit, unsaturated fats can be used to replace saturated fats. Recommended daily intake of cholesterol is less than 300 mg, especially for ASCVD high-risk patients. The total fat caloric intake should be limited to 20%–30% of the total caloric intake.

[figure not shown]
4.4.2 Controlling weight: Obesity is an important risk factor for dyslipidemia. Energy intake in overweight or obese people with dyslipidemia should be lower than energy consumption to prevent weight increase. The goal is to reduce weight gradually until a normal state is reached. Reducing the total amount of daily caloric intake (daily reduction of 300–500 kcal), improving the diet style, and increasing physical activities can reduce weight by more than 10% for overweight and obese people. It is recommended that patients maintain a healthy weight.

4.4.3 Physical activity advice: It is recommended that patients do moderate-intensity exercises, at least 30 minutes per day for 5 days per week. ASCVD patients should do loading activities first to assess whether they are tolerable, and then do physical activities.

4.4.4 Smoking cessation: Smoking cessation and effective reduction of exposure to second-hand smoke are beneficial to prevent ASCVD and increase serum HDL-C levels.

All smokers can be assisted in the clinics, inquire about smoking cessation through hotlines, or take medication to help with smoking cessation.

4.4.5 Restrictions on drinking: Moderate drinking (male: 20-30 g of ethanol per day, female: 10 - 20 g of ethanol per day) can increase serum HDL-C level. However, even a small amount of drinking can increase TG in patients with high TG. There is no convincing evidence that alcohol can increase cardiovascular disease. It is recommended that patients limit drinking.

Biochemical tests: routine blood test, liver function tests including transaminases, uric acid, FBS, FINS, lipid profile.

Physical examinations: waist circumference, hip circumference, blood pressure, heart rate, BMI

Imaging: abdominal color doppler ultrasound, Fibrotouch

5. Expected results:

1) The liver biochemical parameters and other clinical parameters in NAFLD patients will positively correlate with SIBO and intestinal mucosal barrier function.

2) Compound Zhenzhu Tiaozhi capsules will effectively improve liver function (intrahepatic fat content, liver biochemical markers, NAFLD-FS) and related serological parameters (improvement of dyslipidemia and insulin resistance) in NAFLD patients; Compound Zhenzhu Tiaozhi capsules will effectively improve the SF-36 score and reduce the risk of ASCVD in patients with NAFLD.

3) Compound Zhenzhu Tiaozhi capsules will be superior to conventional drugs (simvastatin and metformin) in terms of improving liver biochemical markers and related serological parameters, SF-36 score, and risk stratification of ASCVD.

4) All assessed items of NAFLD patients (liver: intrahepatic fat content, liver biochemical parameters, NAFLD-FS; and its related serological indicators: dyslipidemia, insulin resistance; SF-36 score; and risk stratification of ASCVD) will be positively associated with SIBO and improved function of the intestinal mucosal barrier.

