#### 4.2 Secondary endpoints:

(1) *Serum triglyceride*

(2) *Serum cholesterol*

(3) *Serum lipoproteins:* chylomicron (CM), very-low-density lipoprotein (VLDL), low-density lipoprotein (LDL), and high-density lipoprotein (HDL).

(4) *Hydrogen/methane breath testing:* breath testing for SIBO.

(5) *Intestinal mucosal barrier:* detect levels of diamine oxidase (DAO), D-lactic acid (D-lac), and lipopolysaccharide (LPS), and combine with the clinical manifestations to evaluate the function of the intestinal mucosal barrier.

(6) *Quality of life (SF-36 Scores):* The quality of life of the patients before and after treatment will be assessed using SF-36 scores and compared to assess the improvement.

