4.4. To evaluate the therapeutic effects of Compound Zhenzhu Tiaozhi capsules on NAFLD

1) To assess whether the content of intrahepatic fat will decrease after 1 month, 3 months, and 6 months of Compound Zhenzhu Tiaozhi capsule therapy.

i. Compare the therapeutic effects of Compound Zhenzhu Tiaozhi capsules at 1 month, 3 months, and 6 months with the baseline (pre-vs.post-therapeutic effects of Compound Zhenzhu Tiaozhi capsules).

ii. Compare the therapeutic effects in the Compound Zhenzhu Tiaozhi capsule group with that of the other three groups at parallel time points (Compound Zhenzhu Tiaozhi capsules vs. Conventional drugs).

2) To assess whether NAFLD-FS will be alleviated after 1 month, 3 months, and 6 months of Compound Zhenzhu Tiaozhi capsule therapy.

i. Compare the therapeutic effects of Compound Zhenzhu Tiaozhi capsules at 1 month, 3 months, and 6 months with the baseline (pre- vs. post-therapeutic effects of Compound Zhenzhu Tiaozhi capsules).

ii. Compare the therapeutic effects in the Compound Zhenzhu Tiaozhi capsule group with those of the other three groups at parallel time points

(Compound Zhenzhu Tiaozhi capsules vs. Conventional drugs).

3) To assess whether insulin resistance will be improved after 1 month, 3 months, 6 months of Compound Zhenzhu Tiaozhi capsule therapy.

- i. Compare the therapeutic effects of Compound Zhenzhu Tiaozhi capsules at 1 month, 3 months, and 6 months with the baseline (pre- vs. post-therapeutic effects of Compound Zhenzhu Tiaozhi capsules).
- ii. Compare the therapeutic effects in the Compound Zhenzhu Tiaozhi capsule group with those of the other three groups at parallel time points (Compound Zhenzhu Tiaozhi capsules vs. Conventional drugs).

4) To assess whether the lipids profile in peripheral blood and liver biochemical parameters (ALT, AST, GGT) will be reduced after 1 month, 3 months, and 6 months of Compound Zhenzhu Tiaozhi capsule therapy.

- i. Compare the therapeutic effects of Compound Zhenzhu Tiaozhi capsules at 1 month, 3 months, and 6 months with the baseline (pre- vs. post-therapeutic effects of Compound Zhenzhu Tiaozhi capsules).
- ii. Compare the therapeutic effects in the Compound Zhenzhu Tiaozhi capsule group with those of the other three groups at parallel time points (Compound Zhenzhu Tiaozhi capsules vs. Conventional drugs).

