The early symptoms of NAFLD are not obvious and almost have no impact on daily life. As it is difficult to effectively assess whether patients have benefited from treatment by evaluating symptoms, the investigators will use the SF-36 questionnaire. The questionnaire will be administered at the time of patient enrollment, and at 1 month, 3 months, and 6 months after treatment. To determine whether drug intervention during the early stage of NAFLD can improve symptoms, the scores of the SF-36 before and after treatment will be compared in the following groups: TLC + metformin, TLC + Compound Zhenzhu Tiaozhi capsules, TLC + simvastatin, and TLC. The four groups will also be compared to one another.

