3.4 Sample Size

A total of 196 patients will be enrolled in this study. The sample size is estimated as follows:

Previous studies have reported that the efficiency rate of metformin and simvastatin in the treatment of NAFLD is 36-52%. We hypothesize that the efficiency rate of Compound Zhenshu Tiaozhi capsules will increase by 25% compared to standard drugs.

Statistical calculation: $P_1 = 69\%$, $P_2 = P_3 = 44\%$, $P_4 = 10\%$, $\delta = P_1 - P_2 = 25\%$, with $\alpha = 0.05$,

power = 0.80, and a bilateral test, $n = \frac{\chi_{\alpha}^2 + \chi_{\beta}^2}{w^2}$, of which $w = \sqrt{\sum_{i=1}^m \frac{(P_{t,i} - P_{c,i})^2}{P_{c,i}}}$, thus n will be equal to 44.

Assuming that the rate of loss to follow up is 10%, each group will require 49 cases. Therefore, a total of 196 cases will be required for the four groups.

4. Evaluation of the Efficacy of Parameters and Predictors

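### Expected superiority over simvastatin and metformin is framed on about 11 non-primary measures, with no stated rule for what counts as superior and no visible error control

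*Protocol*

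**What the plan says.** **The expectation.** Protocol section 5 (Expected results), item 3: "Compound Zhenzhu Tiaozhi capsules will be superior to conventional drugs (simvastatin and metformin) in terms of improving liver biochemical markers and related serological parameters", followed by SF-36 score and ASCVD risk stratification. Item 2 shows what the serological part covers: "related serological parameters (improvement of dyslipidemia and insulin resistance) in NAFLD patients". Item 2 also names intrahepatic fat; item 3 does not.

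**The planned comparisons.** Protocol 4.4, items 2 to 4 (fibrosis score, insulin resistance, lipids with liver enzymes), each include the instruction "Compare the therapeutic effects in the Compound Zhenzhu Tiaozhi capsule group with those of the other three groups at parallel time points", at months 1, 3 and 6. Protocol 4.6 plans the same three visits for ASCVD risk and a comparison with the conventional drugs. The SF-36 paragraph (numbered 3.5, after 4.6) has the same visits and says "The four groups will also be compared to one another".

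**The primary and the sizing.** The primary endpoint is a drop of at least one fat attenuation level (Protocol 4.1, SAP 4.1). The superiority hypothesis used for sizing concerns that response rate: "We hypothesize that the efficiency rate of Compound Zhenshu Tiaozhi capsules will increase by 25% compared to standard drugs" (SAP 3.4), that is 69% v 44%, two-sided alpha 0.05. No other alpha appears in the text.

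**Status of the other measures.** Lipids and SF-36 are secondary endpoints (Protocol 4.2, SAP 4.2). Liver enzymes, insulin resistance and ASCVD class are in neither endpoint list, but SAP 2.3 makes liver biochemistry and insulin resistance secondary objectives alongside lipids.

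**Visits for liver biochemistry.** Protocol 4.4 item 4 has months 1, 3 and 6. SAP section 5 has admission and month 6 only.

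**The concern.** The documents do not say which measure, which visit, or how many of the two drugs must be beaten before the capsules are called superior. Nothing visible makes a secondary comparison conditional on the primary result. With many measures, two comparators and up to three visits, some comparison will often favour the capsules by chance. The trial could then miss its liver-fat comparison while a report points to one lipid, enzyme, quality-of-life or risk-class result as meeting item 3. Such a claim would have no 5% error guarantee, and the sample size was not set for it.

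**Working it through.** **1. The plan's own figures.** The sample size is the only place where an error rate is used. The dropout step reproduces: 44/0.9 = 48.9, so 49 per group, and 4 × 49 = 196. The 44 does not: a two-sided 0.05 test of 69% v 44% with power 0.80 needs 61 per group. That is a separate problem. The false-positive chances below are computed under no difference and do not depend on n.

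**2. Counting measures in item 3.**
- Liver enzymes: ALT, AST, GGT (Protocol 4.4 item 4) = 3.
- Lipids: "serum lipid profile (triglyceride, very low density lipoprotein, total cholesterol, low density lipoprotein, high density lipoprotein" (Protocol, Prescriptions 4.2) = 5. Chylomicron, in the secondary list, would make 6.
- Insulin resistance = 1; SF-36 as one score = 1; ASCVD class = 1.

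Total: 3 + 5 + 1 + 1 + 1 = 11 (12 with chylomicron). Against two drugs this is 11 × 2 = 22 tests at month 6 and 22 × 3 = 66 over three visits.

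**3. Reference values for one prespecified measure and visit.** A two-sided 5% test favours the capsules by chance with probability 0.025. The two contrasts share the capsule arm, so with equal arms their correlation is 0.5, and the chance of beating both drugs is about 0.005. The chance of beating at least one is 0.025 + 0.025 − 0.005 = 0.045.

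**4. Independent tests, as an upper bracket.** 1 − 0.975^22 = 43%; 1 − 0.975^66 = 81%. The real tests are correlated, so these are too high.

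**5. Correlated tests, by simulation.** Three arms with equal true means on every measure; each arm's standardised means drawn as multivariate normal; z = (capsule − drug)/√2; a win is z > 1.96. The documents give no correlations. Those used are assumptions: 0.5 between measures (range 0.2 to 0.8) and 0.5 to 0.7 between visits.

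| What counts as superior | Month 6 only | Months 1, 3, 6 |
|---|---|---|
| One win against either drug, correlation 0.5 between measures | 25% | 43–49% |
| Same, correlation 0.8 to 0.2 between measures | 15–34% | 28–63% |
| Both drugs beaten on the same measure and visit, correlation 0.5 | 4% | 8–9% |
| Every measure won against both drugs | about 0 | about 0 |

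**6. Sensitivity to the liver biochemistry schedule.** With enzymes tested only at month 6, as SAP section 5 has it, the three-visit either-drug figure falls from 44% to 40% (correlation 0.5 between measures, 0.7 between visits).

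**7. Sensitivity to counting.** One test for each of five domains (liver markers, lipids, insulin resistance, SF-36, ASCVD) at month 6 gives about 16% for any win and about 2% for beating both drugs in the same domain.

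**The case against.** A reader might infer that the plan permits a superiority claim with a 25–50% false-positive chance. The documents do not support that. Item 3 is a forecast among other forecasts, and no passage says that a single p < 0.05 on any measure, at any visit, against either drug is enough. The sentence names both drugs and joins its domains with an *and*; read strictly, the chance is far smaller. This stands, and it is why the larger figures are given only as conditional.

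A reader might also take item 3 as the protocol's definition of superiority over the active drugs. It is not: the sized hypothesis is the liver-fat response rate, and SAP primary objective 1 covers the comparison with both drugs.

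Third, it is tempting to say that liver enzymes and insulin resistance have no status in the plan. They are missing from the endpoint lists, but SAP 2.3 makes them secondary objectives. Nor can one say that error control is absent altogether, because the SAP text stops at baseline characteristics with no efficacy-testing section visible.

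The test count is also partly a choice. ASCVD class is derived partly from cholesterol values already counted, and grouping into domains lowers the figures.

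What these points do not remove is the gap itself. The strict two-drug reading is not written down either, and 4% against a reference of 0.5% is still about eight times higher (4/0.5); 8–9% is 16 to 18 times higher. The SAP's use of exploratory language does not help, since it is applied to the primary objective as well.

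**Conclusion.** The concern holds in a limited form. The available text anticipates superiority over two active drugs on about 11 non-primary measures, plans the between-arm comparisons at up to three visits, and leaves the criterion for superiority undefined, with no gate, ranking, designated visit or exploratory label. The size depends on how the gap is filled. It is about 25% (month 6) to 43–49% (three visits) if one win against either drug suffices, and about 4% to 8–9% if both drugs must be beaten on the same measure and visit. These figures rest on no true difference on any measure, two-sided 5% tests, the assumed correlations and a count of 11. The finding is confined to the text available, which ends at SAP 9.5.

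**What to change.** - **Expected result 3:** reword it so that superiority over metformin and simvastatin is claimed only from the month 6 fat attenuation response. State that both drugs must be beaten, or apply Holm across the two comparisons (0.05/2 = 0.025 for the smaller p-value). Without this, the primary itself remains open to three visits and two drugs.
- **SAP 4.2:** report the other between-arm comparisons (lipids, liver enzymes, fibrosis score, insulin resistance, gut markers, SF-36, ASCVD class) as secondary or exploratory differences with 95% confidence intervals and no superiority claim. If a confirmatory secondary claim is wanted, name a few month 6 measures, test them only after the primary succeeds, and use Holm across measures and drugs.
- **Liver biochemistry visits:** reconcile Protocol 4.4 item 4 with SAP section 5.

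**Cost.** Wording only for the claim and labels; no new data. An isolated p < 0.05 on a secondary measure can no longer be called superiority. The sizing covers one comparison of 69% v 44%, so either two-drug rule lowers power. For example, a two-sided 0.025 test needs 74 per group for power 0.80, against 61 at 0.05. The sponsor should weigh this when the sample size section is revisited.
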